13.1.6.2 Adverse Events

All AEs will be coded using the Medical Dictionary for Regulatory Activities (MedDRA), Version 20.1 or higher.

Treatment-emergent AEs are defined as:

- AEs with onset at the time of or following the start of treatment with IP through the Follow-up Visit or Early Termination Visit, whichever occurs first, or
- AEs starting prior to the start of treatment but increasing in severity or relationship at the time of, or following, the start of treatment with IP through the Follow-up Visit or Early Termination Visit, whichever occurs first.

The number and percentage of subjects with AEs will be displayed by each treatment group in the Double-blind Period and overall in the OLE by system organ class and preferred term. Summaries of AEs by severity and relationship to IP will also be provided. Serious adverse events and AEs resulting in discontinuation of IP will be summarized separately in a similar manner. Subject listings of AEs, SAEs, and AEs causing discontinuation of IP will be produced.

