- a. Upon signing informed consent and entering the Screening Period, subjects will stop using physical and medical treatments for LI, including balneotherapy, and may begin to washout prohibited topical and systemic treatments with designated washout periods, as applicable. Washout may be up to 3 months, as necessary. During washout, subjects may continue taking usual care of visible skin (face and scalp) for cosmetic reasons and of extremities (hands and feet) to avoid functional consequences on walking or moving their fingers. Subjects may shower, but not bathe or swim during the Screening Period. After completing any necessary washout of prohibited medications, subjects will return to the site to complete the study eligibility requirements.
- b. Day 90 procedures should be conducted for subjects who terminate the study early. If a subject discontinues IP, but continues to attend clinic visits, Day 90 will occur as scheduled. Day 90/Week 12 will be the first visit of the OLE for subjects who choose to continue (subjects will have up to 7 days to decide to sign the ICF and begin the OLE). Subjects who decide to continue into the OLE will have the following additional procedures: 1) sign informed consent; 2) will be weighed; 3) will be instructed on study drug application; 4) will be given new diaries, and 5) will be provided with study drug.
- c. A Follow-up telephone call will be made within 14 days after Day 90 to subjects who choose not to continue into the OLE.
- d. Limited physical examination to include HEENT, cardiorespiratory, abdomen, range of motion.
- e. IGA: 0 = clear; 1 = almost clear; 2 = mild; 3 = moderate; 4 = severe.
- f. VIIS scale for each body area: chest/abdomen, back, legs, and arms, for a possible overall score = 16.
- g. Roughness (0-4 scale);
- h. Palm/sole fissuring assessment: present/absent/number/pain (0-3 scale).
- i. Photography will be performed at sites with the capability for subjects who sign a photographic ICF. A central reader who will not be an investigator in the study will review the photographs to assess consistency of investigator scoring of LI severity as a quality check.
- j. ECG to be conducted at Screening, Baseline, Day 30, and Day 90 for all subjects. Subjects in the PK substudy will also have postdose ECGs at each serial blood draw on Day 1 and Day 30.
- k. Subjects must be fasting (i.e., at least 8 hours)

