6.2. Secondary Objectives

The secondary objectives are as follows:

- To assess systemic exposure to trifarotene and its major metabolites after topical application of the investigational product (IP) on up to 90% BSA twice weekly.
- To assess safety for up to 24 weeks of dosing with open-label trifarotene cream HE1 200 µg/g.

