8.3. Premature Subject Withdrawal

All subjects will be advised that they are free to withdraw from participation in this study at any time, for any reason, and without prejudice. The investigator should make every reasonable attempt to keep subjects in the study; however, subjects must be withdrawn from the study if they withdraw consent to participate. Investigators must attempt to contact subjects who fail to attend scheduled visits by telephone or other means to exclude the possibility of an AE being the cause of withdrawal. Should this be the cause, the AE must be documented, reported, and followed as described in Section 11.2.

The sponsor reserves the right to request the withdrawal of a subject due to protocol deviations or other reasons.

The investigator also has the right to withdraw subjects from the study at any time for lack of therapeutic effect that is intolerable or otherwise unacceptable to the subject, for intolerable or unacceptable AEs, intercurrent illness, noncompliance with study procedures, administrative reasons, or in the investigator's opinion, to protect the subject's best interest.

If a subject is withdrawn before completing the study, the reason for withdrawal and the date of discontinuation will be recorded on the appropriate page of the electronic case report form (eCRF). Whenever possible and reasonable, the evaluations that were to be conducted at the completion of the study should be performed at the time of premature discontinuation.

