10.2.3 Follow-up Telephone Call (± 14 days after Day 90) – Only Subjects Who Do Not Continue into Open-label Extension

Clinic staff will telephone subjects who choose not to continue into the Open-label Extension within 14 days after Day 90 to assess any ongoing AEs.

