11.1.6 Treatment-Emergent Adverse Events

An AE is defined as treatment emergent if the first onset or worsening is after the first application of IP (trifarotene or vehicle) and not more than 14 days after the last application of IP.

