11.2. Event Assessment and Follow-up of Adverse Events

The occurrence of an AE or SAE may come to the attention of study personnel during study visits and interviews of a study participant presenting for medical care or upon review by a study monitor.

All reported AEs, including local and systemic AEs not meeting the criteria for SAEs, will be captured on the appropriate eCRF. Information to be collected includes event description, time of onset, clinician's assessment of severity, relationship to study product (assessed only by those with the training and authority to make a diagnosis), and time of resolution/stabilization of the event. All reported AEs occurring while on study must be documented appropriately regardless of relationship. All reported AEs will be followed to adequate resolution.

Any medical condition that is present at the time that the participant is screened will be considered as baseline and not reported as an AE. However, if the study participant's condition deteriorates at any time during the study, it will be recorded as an AE.

Changes in the severity of a reported AE will be documented to allow an assessment of the duration of the event at each level of severity to be performed. AEs characterized as intermittent require documentation of onset and duration of each episode.

Study clinic personnel will record all reportable events with start dates occurring any time after informed consent is obtained until 14 (for nonserious AEs) or 30 days (for SAEs) after the last day of study participation. At each study visit, the investigator will inquire about the occurrence of AE/SAEs since the last visit. Events will be followed for outcome information until resolution or stabilization.

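### Amendment 2 ends the treatment-emergent adverse event window at two different points, and open-label adverse events are fixed for display overall only

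*Protocol*

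**What the plan says.** The protocol file holds more than one version. Amendment 2 contains both sections in question. Section 11.1.6 counts an event whose onset or worsening is after the first application and "not more than 14 days after the last application of IP". Section 13.1.6.2, which defines TEAEs for the analysis, counts events "through the Follow-up Visit or Early Termination Visit, whichever occurs first". The version before Amendment 2 carries the same pair. The later version (Day 90 wording, COVID-19 appendix) repeats 13.1.6.2 unchanged, but its Section 11 is not in the text available.

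Related provisions:

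- **Timing of the ET evaluations (8.3):** where possible, "the evaluations that were to be conducted at the completion of the study should be performed at the time of premature discontinuation".
- **Stopping drug but staying in the study (footnote to Table 2-1):** "If a subject discontinues IP, but continues to attend clinic visits, Day 90 will occur as scheduled".
- **Recording of events (11.2):** "until 14 (for nonserious AEs) or 30 days (for SAEs) after the last day of study participation".
- **Follow-up call for subjects not entering the OLE (10.2.3):** the text places it "within 14 days after Day 90 to assess any ongoing AEs". The section heading gives plus or minus 14 days, and 10.1.1 sets follow-up at 14 days after the last application.
- **OLE display (13.1.6.2):** events are shown by treatment group in the Double-blind Period and "overall in the OLE by system organ class and preferred term".
- **Secondary objective (6.2):** "To assess safety for up to 24 weeks of dosing with open-label trifarotene cream HE1" at 200 µg/g. The OLE itself lasts 12 weeks.

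**The concern.** Safety is part of the primary objective, and the TEAE table is its main summary. With two definitions in force, the count depends on which section the programmer follows. Section 13.1.6.2 ties the end of the window to a visit date, so subjects with the same last application can have different observation time after treatment. Events recorded after an ET Visit can meet 11.1.6 and still be left out of the summaries.

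The OLE display is a second, separate matter. All OLE subjects receive the same treatment, but they arrive from three double-blind arms. Section 11.3.1 says local application-site events occur particularly when treatment begins. Former vehicle subjects are beginning; former active subjects have had about 12 weeks already. An overall rate describes neither group well, and it does not isolate the only subjects who can reach 24 weeks at 200 µg/g.

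**Working it through.** The plan states no figure for this point, so the check compares the texts and measures the gap between the two windows.

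**1. Where the windows agree.** For OLE completers, 10.2.4.7 places the Follow-up Visit 14 days after the last application, so both definitions end together. The stated maximum study duration fits this: 35 + 180 + 14 = 229 days.

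**2. Where they differ: early termination.** Let g be the number of days from the last application to the ET Visit. Section 13.1.6.2 ends at g and 11.1.6 ends at 14, so the difference is g − 14.

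| g (days) | 13.1.6.2 minus 11.1.6 (days) |
|---|---|
| 1 | −13 |
| 4 | −10 |
| 7 | −7 |
| 14 | 0 |
| 30 | +16 |

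The ET Visit includes a PK sample (10.2.2.7), and PK visits must be at least 24 hours after the last application (9.2). So g is at least 1 and the usual maximum loss is 14 − 1 = 13 days. A subject who stops drug, keeps attending and terminates more than 14 days later gets a longer window under 13.1.6.2.

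**3. How many subjects.** 120 / 3 = 40 per arm. The allowance in 13.2 is 20% for drop-out and nonevaluable subjects together: 0.20 × 40 = 8 per arm, 24 in all. This is an upper limit, reached only if every one of them is an early termination.

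**4. How many events.** The documents give no event rate. Assume 0.05 to 0.20 new or worsening events per subject per 14 days, and g from 1 to 4 days. Events left out = 24 × rate × (14 − g) / 14.

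- Low: 24 × 0.05 × 10 / 14 = 0.9
- High: 24 × 0.20 × 13 / 14 = 4.5

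That is about 1 to 4 or 5 events in the whole trial.

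**5. The follow-up call.** Suppose the last application is on Day 89, which is 24 hours before a Day 90 visit. The 11.1.6 window then runs to Day 89 + 14 = Day 103. A call on Day 91 satisfies the text of 10.2.3 but comes 12 days before that window closes, and the call is meant for ongoing events. Read literally, the heading would also permit a call before Day 90.

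**6. The 24-week objective.** A 12-week OLE cannot give 24 open-label weeks. Twenty-four weeks at 200 µg/g needs 12 double-blind weeks plus 12 OLE weeks on that concentration. Only one of the three arms can supply this: at most about 40 subjects, or 40 × 0.80 = 32 if 20% drop out.

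**The case against.** **The versions differ.** Section 13.1.6.2 is in the latest text, but 11.1.6 is visible only in Amendment 2 and the version before it. This stands: the contradiction is shown within Amendment 2 and cannot be shown for the later version.

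**A reader might infer that the analysis window biases the comparison against finding a safety difference.** The documents do not support that. A reaction that causes termination starts before the ET Visit and is inside the window; only events starting or worsening afterwards are left out. Local reactions are first met with reduced or interrupted application on the affected area (9.4). No termination rate by arm is given, no inferential safety analysis is planned (13.1.6), and the sign of the difference depends on g.

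**A reader might also infer that late serious events never reach the SAE tables.** Section 13.1.6.2 summarises SAEs separately and lists AEs and SAEs without limiting these displays to treatment-emergent events. An SAE 15 to 30 days after the last application would fall outside 11.1.6 as well.

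**Events are still recorded.** This also stands. Section 11.2 sets the recording period independently of both definitions and of the call. The loss is from the summaries.

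**The OLE display may be extended in the SAP.** That is possible, and local tolerability is already to be summarised by period, treatment group and visit (13.1.6.1). Showing events overall is a presentation choice, not a contradiction. But the protocol names only that display for OLE adverse events, and its own objective needs more.

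**Conclusion.** The two TEAE definitions in Amendment 2 are incompatible and need reconciling. The effect is small: a few events at most, under the assumed rates and gaps, and in either direction depending on when the ET Visit falls. The ceiling of 8 subjects per arm rests on treating the whole drop-out/nonevaluable allowance as early termination. The case for change is that the definition of a main safety summary should not be open to choice and that correcting it costs little.

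Showing OLE events by prior arm is a worthwhile addition on the protocol's own reasoning about when local events occur. The wording of 6.2 does not match the length of the OLE and should be brought into line with it.

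**What to change.** 1. Use one TEAE window in 11.1.6 and 13.1.6.2: onset or worsening from the first application to 14 days after the last application, with double-blind tables cut at the first OLE application. Check that 13.1.6, which runs the double-blind safety analysis through Week 12 (Day 90 in the later version), agrees. Confirm that Section 11 of the later version carries the same window. For subjects whose ET Visit is more than 14 days after the last application this shortens the window (by 16 days at g = 30), so keep later events in the listings.
2. Reconcile the heading and text of 10.2.3 with each other and with the follow-up stated in 10.1.1.
3. Show OLE adverse events by randomised double-blind arm as well as overall, so that the 200-to-200 sequence can be read separately.
4. Reconcile the objective in 6.2 with the 12-week OLE.

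The cost is protocol and SAP wording plus table columns. Item 2 may also change the timing of a call, which is a procedural amendment. No new visits or subjects are needed.

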13.1.6.3 Clinical Laboratory Evaluations

Descriptive summaries (mean, SD, median, minimum, and maximum) of actual (absolute) values and changes from baseline values will be presented for clinical laboratory values for each treatment group at each time point in each period.

The number of subjects with clinical laboratory values categorized as below, within, or above normal ranges will be tabulated showing change from baseline (shift tables) for each clinical laboratory parameter by treatment group and by study visit in each period.

Laboratory values that are outside the normal range will also be flagged in the data listings and presented with the corresponding normal ranges. Any out-of-range values that are identified by the investigator as being clinically significant will also be shown in a data listing.

13.1.6.4 Vital Signs

Descriptive summaries (mean, SD, median, minimum, and maximum) of actual values and changes from baseline will be calculated for SBP, DBP, and pulse for each period.

The number of subjects with vital signs values categorized as below, within, or above normal ranges will be tabulated showing change from baseline (shift tables) for each parameter by period, by treatment group and by study visit. Pre and post-treatment values may also be presented with an analysis of mean changes from baseline.

13.1.6.5 Twelve-lead Electrocardiograms

The number and percentage of subjects with normal and abnormal ECG findings will be summarized for each treatment group at each time point in each period. Abnormal results will be grouped as clinically significant and not clinically significant.

A comparison of QT results will be presented. Summary statistics will be displayed by period, by treatment group, and by visit for QT and the QT interval corrected for heart rate (QTc) calculated using Fridericia's QT correction methods.

Descriptive summaries (mean, SD, median, minimum, and maximum) will be presented for ECG measures of PR interval, QRS interval, QT interval, QTcF interval (Fridericia's correction methods), and HR for each treatment group at each time point in each period.

13.1.6.6 Physical Examination Findings

The number and percentage of subjects with normal and abnormal findings in the complete physical examination will be displayed for each treatment group in each period.

13.1.7 Interim Analysis

No interim analyses are planned.

13.2. Sample Size Determination

Accounting for a 20% drop-out/nonevaluable rate, a total sample size of 120 subjects randomized in a 1:1:1 ratio to 2 active trifarotene cream HE1 arms and a vehicle cream arm will provide >80% power to detect a difference between each separate trifarotene cream HE1 arm (32 evaluable subjects) and the vehicle cream arm (32 evaluable subjects) 2-sided Fisher's Exact Test assuming a 70% success rate and a 40% success rate, respectively. This study is not powered to detect a difference between the 2 active arms.

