13. STATISTICS

13.1. Statistical Analysis

This section presents a summary of the planned statistical analyses. A SAP that describes the details of the analyses to be conducted will be written prior to database lock.

Unless otherwise indicated, all testing of statistical significance will be two-sided, and a difference resulting in a P value of ≤ 0.05 will be considered statistically significant.

Summary statistics will be provided for the variables described below. For continuous variables, these statistics will include the number of subjects, mean, standard deviation (SD), median, minimum, and maximum. For categorical variables, these statistics will include the number and percentage of subjects in each category.

The primary analysis period is the first 90 days of treatment (i.e., the Double-blind Period). Overall unblinding will take place at the end of the Double-blind Period of the study only after the database is locked. A second analysis will take place for endpoints assessed from Day 90 through the OLE Period. The baseline for the safety and efficacy parameters will be measured at Visit 1 or Visit 2, per the Schedule of Events for both the Double-blind Period ([Table 2-1](#)) and OLE ([Table 2-2](#)).

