13.2. Sample Size Determination

Accounting for a 20% drop-out/nonevaluable rate, a total sample size of 120 subjects randomized in a 1:1:1 ratio to 2 active trifarotene cream HE1 arms and a vehicle cream arm will provide >80% power to detect a difference between each separate trifarotene cream HE1 arm (32 evaluable subjects) and the vehicle cream arm (32 evaluable subjects) using a 2-sample t-test assuming a mean difference of at least 1.0 and a standard deviation of 1.4 or lower. This study is not powered to detect a difference between the 2 active arms.

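### The stated >80% power is wrong: the named Fisher's exact test with 32 evaluable subjects per arm has about 62% power for 70% versus 40%

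*Protocol*

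**What the plan says.** Section 13.2 (Sample Size Determination) plans "a total sample size of 120 subjects randomized in a 1:1:1 ratio", allows for 20% drop-out or nonevaluable subjects, and states that this "will provide >80% power to detect a difference between each separate trifarotene cream HE1 arm (32 evaluable subjects) and the vehicle cream arm". The test and rates are given as "2-sided Fisher's Exact Test assuming a 70% success rate and a 40% success rate, respectively". The sizes on both sides of each comparison are also explicit: "each separate trifarotene cream HE1 arm (32 evaluable subjects) and the vehicle cream arm (32 evaluable subjects".

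Section 13.1 supplies the rest: "all testing of statistical significance will be two-sided", and "a difference resulting in a P value of ≤ 0.05 will be considered statistically significant".

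The same power statement stands in Section 13.2 and in the synopsis of the Amendment 2 text. The version before Amendment 2 has the same 120 randomized and 32 evaluable per arm with the same power claim, but "using a 2-sample t-test assuming a mean difference of at least 1.0 and a standard deviation of 1.4 or lower".

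**The concern.** The protocol gives every input for its power figure, so the figure can be checked without the SAP. A 30-point difference in success rates around the middle of the scale usually needs more than 40 subjects per arm for 80% power, and Fisher's exact test is conservative at this size. A claim of more than 80% with 32 per arm therefore looked too high.

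This is the only sample-size justification for the primary efficacy endpoint. Readers would take it that, if a dose works as assumed, the study misses it at most one time in five. If the true risk is nearly two in five for each dose, a non-significant result for one dose would be read as stronger evidence against that dose than it is. This matters because Sections 5.2 and 7.3 say that the study is to help determine which of the two doses is most effective.

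**Working it through.** **Inputs**

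| Input | Value | Source |
|---|---|---|
| Randomized | 120, in 1:1:1 | 13.2 |
| Loss | 20% | 13.2 |
| Evaluable per arm | 32 | 13.2 |
| Success rates | 70% active, 40% vehicle | 13.2 |
| Test | two-sided Fisher's exact | 13.2 |
| Significance level | two-sided, 0.05 | 13.1 |

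**Step 1. Dropout arithmetic.** 120 / 3 = 40 per arm, and 40 × (1 − 0.20) = 32. This part is correct.

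**Step 2. Power of the named test.** With X successes among 32 active and Y among 32 vehicle subjects,

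Power = Σₓ Σᵧ Bin(x; 32, 0.70) × Bin(y; 32, 0.40) × I[Fisher two-sided p(x, y) ≤ 0.05].

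Summing over all 33 × 33 tables gives **61.9%**. The stated figure of more than 80% is not reproduced.

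**Step 3. Check by hand with the pooled z approximation, which is more favourable than Fisher's test.**
- Mean rate: (0.70 + 0.40) / 2 = 0.55.
- Standard error under the null: √(2 × 0.55 × 0.45 / 32) = 0.1244.
- Standard error under the alternative: √((0.70 × 0.30 + 0.40 × 0.60) / 32) = 0.1186.
- z = (0.30 − 1.96 × 0.1244) / 0.1186 = 0.474, so power is about 68.2%.

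**Step 4. Other tests and sizes, all two-sided at 0.05 with 70% versus 40%.**

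| Reading | 32 per arm | 40 per arm (no loss) |
|---|---|---|
| Fisher's exact | 61.9% | 72.5% |
| Pooled z | 68.2% | 78.0% |
| Arcsine | 68.8% | 78.3% |
| Uncorrected chi-square, exact power | 71.3% | 79.6% |
| Unpooled z | 71.6% | 80.7% |

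Pooling both active arms (64 versus 32) gives 78.9% with Fisher's test, but the protocol claims the power for each arm separately.

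**Step 5. Intent-to-treat set with dropouts counted as failures (an assumption; the protocol does not state this rule).** Rates become 0.70 × 0.80 = 56% and 0.40 × 0.80 = 32%, with 40 per arm. Fisher's test then gives 51.3% and the chi-square test 60.4%.

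**Step 6. What 80% would take.**
- At 70% versus 40% with Fisher's test, 47 evaluable per arm gives 78.6% and 48 gives 80.05%. With 20% loss, 48 / 0.80 = 60 per arm, or 180 in total.
- At 32 per arm with vehicle at 40%, an active rate of 76% gives 79.7% and 77% gives 82.2%.

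**Step 7. Where the 32 probably comes from.** For the superseded t-test, the noncentrality is (1.0 / 1.4) × √(32 / 2) = 2.857 on 62 degrees of freedom. Power is 80.3%, which agrees with the claim of more than 80%. The summary of amended sections shows the test and assumptions replaced while 120, 32 and the power claim stayed the same.

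**The case against.** The best defence is that the power sentence is only a planning approximation. The primary population is all randomized subjects, so 40 per arm is a legitimate denominator, and the planned primary analysis is logistic regression, which is less conservative than Fisher's test. On that reading the figures come close: with 40 per arm, the uncorrected chi-square test has 79.6% power and the two-sided unpooled z approximation 80.7%. A one-sided unpooled z-test at 0.05 with 32 per arm also passes, at 81.2%.

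These variants deserve mention, but they do not save the statement. The protocol specifies Fisher's test, two-sided, with 32 evaluable per arm, and each variant above 80% departs from at least one of these. Taking 40 per arm at the full assumed rates also ignores the 20% loss for which the same sentence allows.

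Some limits do stand. Carry-over of the sample size from the t-test plan is an inference, since the protocol does not say why the number stayed. The dropouts-as-failures scenario is illustrative: the protocol asks for the Day 90 assessments at early termination, so some subjects who leave early will have a score. No power was computed for the logistic model itself; the chi-square figures are a proxy. The misstatement affects neither the type I error nor the treatment estimate, and this is a phase 2 study. None of this changes the result for the test and size that the protocol names.

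**Conclusion.** The power statement is wrong as written. With the protocol's own test, rates, size and significance level, power is 61.9% per comparison against a stated figure above 80%. The shortfall is at least 80 − 61.9 = 18.1 percentage points, and the risk of missing the assumed effect is about 38% for each dose instead of less than 20%. No two-sided method examined reaches 80% with 32 per arm.

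The result assumes independent binomial outcomes, a true 70% versus 40%, and each dose tested at the unadjusted two-sided 0.05 level. The 20% loss is taken as removing subjects without changing the success rates. If losses counted as failures, power would be lower still.

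**What to change.** In Section 13.2 and the synopsis, replace the claim of more than 80% power with a correct statement. Suggested wording: *With 32 evaluable subjects per arm, a two-sided Fisher's exact test at the 0.05 level has about 62% power to detect 70% versus 40% in each comparison of an active arm with vehicle.* Alternatively, keep 80% and change the effect: 32 per arm gives at least 80% power for about 77% versus 40% (82.2%; 76% falls just short at 79.7%).

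Add a sentence on power for the planned logistic analysis in the intent-to-treat set. With the planned 20% loss, the chi-square proxy runs from about 60% (losses as failures) to about 71% (losses excluded). It would approach 80% only if all 40 per arm were assessed at the assumed rates. The sentence should name the rule for losses that it uses.

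The cost is one paragraph in the next amendment and matching text in the SAP, and a less favourable figure on record. No change in enrolment is proposed; the 48 evaluable per arm (180 randomized in total) needed for 80% at the stated rates may be out of reach in a rare disease. The study report should then read a non-significant result for either dose in the light of the corrected power.
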